9.4.3 Analysis of the Secondary Endpoint(s)

The secondary endpoints are not dependent on the primary endpoints.

1. Device Use Survey questions that are specific to the functioning of the device are collected as ordinal data on a Likert scale. Data will be presented as the median value with standard deviation for individual question results. Aggregate (summed) results for all questions will be also be assessed using the same methodology. Statistical significance will be determined using Chi-square test. Sub-analysis will be performed based on user subject experience level.
2. Device Use Survey questions that are specific to the healthcare burden associated with the device are collected as ordinal data on a Likert scale. Data will be presented as the median value with standard deviation for individual question results. Aggregate (summed) results for all questions will be also be assessed using the same methodology. Statistical significance will be determined using Chi-square test. Sub-analysis will be performed based on user subject experience level.
3. Patient experience survey results are collected as ordinal data on a Likert scale. Data will be presented as the median value with standard deviation for individual question results. Aggregate (summed) results for all questions will be also be assessed using the same methodology. Statistical significance will be determined using Chi-square test. Sub-analysis will be performed based on patient age, gender, co-morbid conditions, type of airway procedure performed.

Statistical analyses will be performed on all data points, however, a sub-analysis will be performed on participants without any missing data points.

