9 STATISTICAL CONSIDERATIONS

9.1 *Statistical Hypotheses*

We hypothesize that the biocontainment device will be a safe and effective option for performing airway procedures in patients while also providing additional protection during an aerosol generating procedure.

Primary Efficacy Endpoints:

1. We hypothesize that the time to perform an airway procedure with the biocontainment device will be equivalent to time for airway procedure without the biocontainment device. Alternatively, there will be prolonged airway procedures times with the device. This endpoint will be analyzed every two weeks.
2. We anticipate that the number of AEs or ADEs will be low and will also decrease over time. This endpoint will be analyzed on a weekly basis.

Secondary Efficacy Endpoints:

1. We hypothesize that the median Likert ratings for User subject device comfort will be weighted toward “strongly agree”. Alternatively, we will see ratings favoring “neutral” or “disagree” for user subject device comfort.
2. We hypothesize that the median Likert ratings for User subject additional healthcare burden comfort will be weighted toward “strongly disagree”. Alternatively, we will see ratings favoring “neutral” or “agree” on increased healthcare burden.
3. The median Likert ratings for the Patient Experience survey will be weighted toward minimal patient discomfort or anxiety. Alternatively, we will see ratings favoring increased patient discomfort or anxiety inside the device.
3. We anticipate that the median Likert ratings of the patient experience post-survey will indicate overall good user comfort and low levels of anxiety or claustrophobia in the device.

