9.4 Statistical Analyses

9.4.1 General Approach

Descriptive statistics:

- The number of subjects who utilized the protective device will be included; the level of experience and training of user subjects will be included.
- Patient subject baseline demographics, co-morbidities, smoking status, and intubation-related factors will be included.
- Objective data regarding total time for the airway procedure, number of intubation/LMA/extubation attempts, airway device used (i.e. intubation blade used and size of ETT) will be included.
- The user subjects comfort level for device use will be graded on a continuous scale, and the mean comfort level calculated as well as the range.
- The patient subjects comfort level and experience in the device will be graded on a continuous scale, and the mean comfort/experience level calculated as well as the range.
- Categories for various healthcare burdens will be provided as options for participants; the mean for most common burden will be identified; the percentage for each burden subtype will also be identified.

Inferential Tests

- A p-value of 0.05 and 95% confidence interval will be utilized when determining if the protective device results in an improvement in outcomes measures, i.e. a decrease in the number of COVID-19 cases by participants.
- Chi-square testing or ANOVA will be used.

Covariates will be collected on participants, including but not limited to subspecialty training, years of experience as a resident, fellow, or attending, as well as gender.

Assumption of normality of data points will be determined using Q-Q plots. If there are limitations to performing assumptions of normality, then appropriate non-parametric corrections would be performed.

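### Section 9.4.3 tests ordinal survey ratings and summed scores with an unordered chi-square test, without saying what is compared; the cost in power is large mainly for the summed score

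*Combined protocol and SAP*

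**What the plan says.** Section 9.4.3 covers three survey endpoints: user ratings of device function, user ratings of healthcare burden, and patient experience. Each is described as ordinal; for the third the text is "Patient experience survey results are collected as ordinal data on a Likert scale". Each item then gives a median with standard deviation and continues "Aggregate (summed) results for all questions will be also be assessed using the same methodology. Statistical significance will be determined using Chi-square test". It names no trend test, rank test or exact test, and no rule for collapsing categories.

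The sub-analyses follow. For the patient survey: "Sub-analysis will be performed based on patient age, gender, co-morbid conditions, type of airway procedure performed". For the two user surveys: "Sub-analysis will be performed based on user subject experience level". No test is attached to these sentences, and no sentence says what the chi-square test compares.

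Three other places bear on the point:

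- Section 9.1 expects ratings to cluster at one end: "The median Likert ratings for the Patient Experience survey will be weighted toward minimal patient discomfort or anxiety".
- Section 9.4.1 sets the level ("A p-value of 0.05 and 95% confidence interval will be utilized when determining"), allows chi-square or ANOVA, describes comfort as graded on a continuous scale and summarised by a mean, and offers a non-parametric fallback if normality is in doubt.
- Section 9.2 asserts adequate power for the secondary endpoints and concedes that some sub-analyses may be underpowered.

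**The concern.** A Pearson chi-square test treats the rating levels as unordered labels. If one group's ratings move steadily toward the worse end, a test that uses the order puts all its sensitivity into that one direction. Chi-square spreads it over every possible pattern of difference. For one 5-level item this costs 4 degrees of freedom instead of 1. For a summed score with one column per total it can cost up to 20, and most cells become sparse.

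The comparison itself is also left open. Sections 1.3 and 8.1 send the patient survey only to patients randomized to the device, so it has no between-arm contrast. The subgroup contrasts are the only between-group comparisons that can be made with it. What is at stake is whether those comparisons, and the summed score in particular, could show a real difference between patient groups. The endpoints themselves are median ratings, and the choice of test does not change them.

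**Working it through.** **The plan's own figure.** The only sample-size figure is in section 9.2: 1.96² × 0.25 / 0.1² = 3.8416 × 0.25 / 0.01 = 96.04, rounded up to 97. It reproduces. It is a precision calculation for one proportion and gives no power for any survey comparison.

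**Inputs from the documents.** 100 device-arm patients (section 1.3); five rated topics plus free comments in the patient survey (section 8.1); level 0.05 (section 9.4.1).

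**Assumed, because the documents do not give them.** Five levels per item; ratings 45/33/14/6/2% from best to worst, in line with the clustering expected in section 9.1; inter-item correlation 0.5; two groups split 50/50, 70/30 or 85/15, with the smaller group giving the worse ratings; two-sided testing; one response per patient.

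**Expected counts.** Expected count = group size × column share.

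- Single item at 50 per group: 50 × 0.14 = 7, 50 × 0.06 = 3 and 50 × 0.02 = 1. Two of the five levels fall below 5, so 4 of 10 cells. In simulation 29–48% of cells are below 5, depending on split and shift.
- Summed score: totals run from 5 to 25, so 25 − 5 + 1 = 21 columns and 2 × 21 = 42 cells. The average count is 100 / 42 = 2.4. In simulation 71–83% of cells are below 5. A minority are below 1: about 15% at 50/50, and 7–41% across other assumed shapes and splits.

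**Power for the summed score, tabulated by total** (ranges are across repeated simulations; shifts of 0.4 / 0.6 SD on the latent rating scale):

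| Split | Chi-square | Wilcoxon |
|---|---|---|
| 50/50 | 13–16% / 41–44% | 67–70% / 95–96% |
| 70/30 | 24–25% / 52–53% | 59–60% / 91–92% |
| 85/15 | 30–31% / 56% | 41–42% / 72–73% |

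With totals grouped at quartiles (50/50 split only), chi-square power is 47% / 85%. That recovers much of the loss but stays below Wilcoxon.

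**Power for a single item, 50/50.** At odds ratios 2.0 / 2.5 / 3.0, chi-square has 27% / 46% / 64% and Wilcoxon 47% / 70% / 85%. The differences are 20, 24 and 21 percentage points. At uneven splits with skewed ratings the loss is smaller. For example, with a similar skewed shape (50/30/13/5/2%) at 85/15, it is 70% against 77%.

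**Other rating shapes.** With the shift set so that Wilcoxon has about 80% power, and skewed, moderate or uniform ratings, chi-square has 57–70% for an item. For the sum it has 18–22% at 50/50, 19–41% at 70/30 and 23–64% at 85/15.

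**Error rate with no true difference.** For an item, chi-square rejects about 3.5–6% of the time. For the sum it rejects 2.5–3.4% at 50/50 and 70/30 (conservative) and 4–5% at 85/15. Wilcoxon stays near 5%.

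**Analytic cross-check.** Noncentrality 7.85 gives 80% power on 1 df. The same noncentrality gives 60% on 4 df and 31% on 20 df. Restoring 80% would take about 1.5 and 2.7 times the sample.

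**The case against.** **The contrast is inferred.** The chi-square sentence comes before the sub-analysis sentence, and the hypotheses in section 9.1 concern where one group's ratings lie. A reader might take it as settled that chi-square will compare subgroups; the text does not say so. This stands, and it makes the unstated comparison part of the problem. It does not make an unordered test suitable for ordinal data.

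**The phrase about the same methodology may refer only to the median and standard deviation.** It follows that sentence directly. The natural reading still extends the chi-square test to the sum, because the test sentence comes next and is not limited to single questions. One column per total is nonetheless only one way to do it. Grouping the totals would cost less, and the plan specifies neither.

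**The non-parametric fallback in section 9.4.1 might cover this.** It is triggered by doubts about normality. Chi-square assumes no normality, so nothing triggers a change from the test named in 9.4.3. The continuous-scale wording in 9.4.1 conflicts with the ordinal description in 9.4.3 and adds to the need for one clear rule.

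**Low power is already conceded.** Section 9.2 does so, but attributes it to the characteristics of the recruited patients. The loss here comes from the test and is avoidable.

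**Stronger readings.** A reader might infer that most of the power is lost for single items too, or that the summed score is always the least sensitive measure. Neither holds. Single items keep more than half of Wilcoxon's power in every 100-patient setting examined. At 85/15 the sum (30% / 56%) does no worse than a single item (28% / 44%). A reader might also extend the figures to the user surveys. These are repeated daily by 15 to 20 users (sections 5.5 and 8.1), so calculations for 100 independent responders do not carry over. No decision rule in the plan rests on these p-values.

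**Conclusion.** The concern holds in a limited form. Section 9.4.3 names a test that ignores order for data it calls ordinal, appears to apply it to summed scores as well, and leaves the comparison unstated.

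For a patient-survey sum tabulated by total, the loss against a rank test is about 50 percentage points at an even split, about 35–40 at 70/30, and about 10–17 at 85/15. For single items it is a moderate loss of about 20–24 points at an even split, generally less at uneven splits when ratings are skewed, with an error rate close to nominal.

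The direction follows from the nature of the test. The sizes depend on the assumed number of levels, rating shape, correlation, group sizes and tabulation, none of which the documents give. They describe the patient survey only. The change is worth making because it gains power without new data, but the median ratings that form the endpoints are unaffected.

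**What to change.** In section 9.4.3, items 1 to 3:

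- State the comparison for each survey endpoint: which groups, and how they are defined.
- For subgroup comparisons, replace chi-square with a Wilcoxon or Kruskal-Wallis test, or a proportional-odds model with age as a continuous term.
- Analyse the summed score as a score, reporting a difference with its 95% CI, and not as a table of categories.
- For the daily user surveys, use one summary per user or a model with a user random effect. A plain rank test on pooled repeated ratings would not be valid.
- Reconcile the continuous-scale wording in section 9.4.1 with the ordinal description in 9.4.3.

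The cost is a wording change to the plan and slightly more analysis work. The data collected and the sample size do not change.

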1 STUDY SUMMARY

1.1 Synopsis

Title: Aerosol Biocontainment Device (ABCD) with Aerosol Clearance for Aerosol Generating Procedures

Short Title: Aerosol BioContainment Device (ABCD)

Study Description: The primary goal of this study is to assess use of a biocontainment device for planned airway procedures under general anesthesia. This will serve as a platform for using this device as a novel biocontainment and aerosol evacuation system as part of rapid sequence intubation protocols for COVID-19 patients. We hypothesize that airway procedures with the aerosol biocontainment device will be safe and effective with airway procedure times approaching times for airway procedures without the device.

Objectives: The primary objectives of this study are: 1) Assess changes in airway procedure time with and without the biocontainment device as a function of repeated utilization and as a function of patient-associated airway factors (i.e. Mallampati score, hyomental distance, neck mobility, BMI) and user-associated airway factors (i.e. experience of user, airway device used, induction sequence) 2) Assess adverse events, adverse device events associated with biocontainment device use.

Secondary objectives include: 1) Assess the subject's comfort with using the biocontainment device. 2) Assess for additional healthcare and cognitive burden imposed by the device. 3) Survey of patient's post-procedure on experience being inside the device. Exploratory objectives include gathering specific feedback regarding possible design modifications for further iterations and design improvements with the engineering team.

Primary Endpoint: The primary endpoints of this study are:
1. Measuring the time for performing an airway procedure with the biocontainment device when accounting for patient and user-specific factors.
2. Quantifying the number of AEs or ADEs over time to assess device safety.

Secondary Endpoints: The secondary endpoints include:
1. Median Likert ratings from device use survey questions that assess user subject device comfort.
2. Median Likert ratings from device use survey questions that assess user subject healthcare burden with the device.
3. Median Likert rating of the patient questionnaire results to assess patient experience in the device.

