1.3 Schema

Week 1 through Week 4	Enrollment and Training

 • Total n=5 anesthesiologists, 10 CRNAs/anesthesia residents/fellows (user subjects) • Identify user subjects - anesthesiologists and their teams of CRNAs, anesthesia residents and fellows performing planned airway procedures under general anesthesia. • Obtain informed consent from willing user subjects and complete intake questionnaire • Document and record contact information for user subjects • Review user manual and device use. 	
Week 1 through Week 6	Device Use and Assessment

 • Protective device use and aerosol evacuation during airway procedures under general anesthesia on COVID-19-negative patients • Patients (patient subjects) of anesthesiologists participating as user subjects in the study will be recruited on the day of procedure. • Patient subjects will be randomized to intubation with or without the biocontainment device. • Goal of obtaining data from 150 airway procedures under general anesthesia in the device (100 with the device and 50 without the device). • Patient subject Data and data from record of airway procedure will be recorded after each device use • Quality Use Survey, including documentation of any AEs will be completed by user subjects at the end of each day • Patient experience questionnaire completed by patient subject randomized to device use within 1 week after procedure 	

- AE event summary reconciliation and review performed weekly
- Feedback on quality use data use and user suggestions given to engineering team every two weeks
- Interval assessment by the medical director of intubation data from medical record, quality use survey data, including summary of AEs, and preliminary analysis of post-training questionnaire/intake data every two weeks

Week 4 through Week 12	Device Use and Assessment, Final Data Analysis
	
• Continued use and assessment of biocontainment device if needed to meet enrollment numbers• Final Feedback on device use and user suggestions given to engineering team• Final assessment of survey data and device utilization

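### The chi-square in 9.4.3 has no stated null or comparator and does not test the directional Likert hypotheses of 9.1; 9.4.1 and 9.4.3 also disagree on the summary statistic

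*Combined protocol and SAP*

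**What the plan says.** Section 9.4.3 gives the same plan to all three secondary endpoints (user comfort, user-reported healthcare burden, patient experience). The data are ordinal; for patients the wording is "Patient experience survey results are collected as ordinal data on a Likert scale". The summary is "Data will be presented as the median value with standard deviation for individual question results", with the same method for summed scores. Then: "Statistical significance will be determined using Chi-square test". A separate sentence adds sub-analyses, by user experience for the two user surveys and by age, gender, co-morbidity and procedure type for patients.

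The endpoints in the synopsis (1.1) and section 3 are medians, for example "Median Likert rating of the patient questionnaire results to assess patient experience in the device". Section 9.4.1 describes the ratings differently: "The user subjects comfort level for device use will be graded on a continuous scale, and the mean comfort level calculated", with the range, and "The patient subjects comfort level and experience in the device will be graded on a continuous scale", again with mean and range.

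The hypotheses in 9.1 are directional: comfort toward strongly agree, burden toward strongly disagree, patient experience toward little discomfort or anxiety. For comfort and burden, neutral ratings belong to the alternative.

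On who is surveyed, the schema (1.3) says "Patient experience questionnaire completed by patient subject randomized to device use within 1 week after procedure", and 8.1 repeats the restriction to the device arm. The user survey follows each day using the device (8.1) or each device use (8.2).

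**The concern.** A test of significance needs a null. Section 9.4.3 supplies neither a second group nor a reference value, and the 50 planned procedures without the device yield no ratings. Whichever chi-square an analyst chooses, its p-value has to be shown to bear on the claim in 9.1 that ratings lean in a particular direction. The contradictory summaries are a second problem: an analyst cannot follow 9.4.1 and 9.4.3 together, and a standard deviation does not describe spread about the median of an ordinal item. Third, 15 to 20 users supply all the user ratings, so responses from one user are likely to be correlated, and experience varies between users rather than within them.

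At stake are the inferential statements attached to all three secondary endpoints. Section 9.2 says the study should be adequately powered for them, and 9.4.5 includes them in the interim analysis.

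**Working it through.** **The plan's own figure.** The only sample-size calculation (9.2) gives 1.96² × 0.25 / 0.10² = 96.04, so 97. It reproduces. It is a precision calculation for one proportion and gives no power for any chi-square test.

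**Reading 1: one-group goodness of fit.** The plan gives no expected distribution and no Likert counts. I assume 100 ratings on five ordered categories and equal expected counts of 20. The statistic is the sum of (observed − 20)² / 20 on 4 degrees of freedom.

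| Assumed counts, lowest to highest | Chi-square | p | Median |
|---|---|---|---|
| 5/10/20/35/30 | (225+100+0+225+100)/20 = 32.5 | 1.5e-6 | 4 |
| 30/35/20/10/5 | (100+225+0+100+225)/20 = 32.5 | 1.5e-6 | 2 |
| 5/15/60/15/5 | (225+25+1600+25+225)/20 = 105 | 8e-22 | 3 |

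The test cannot separate the first two rows. The smallest p-value goes to the neutral pattern, which 9.1 places under the alternative for comfort and burden.

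**Reading 2: contingency table across the named subgroups.** With the same unfavourable split (20/15/8/5/2) in both of two strata, chi-square is 0 and p = 1. With the same favourable split in both, it is again 0 and p = 1. This asks whether strata differ, not whether ratings are favourable.

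**A summary that does address 9.1.** If the top two categories count as favourable, row 1 gives 35 + 30 = 65%, with simple interval 65 ± 1.96 × √(0.65 × 0.35/100) = 65 ± 9.3 points. Row 2 gives 10 + 5 = 15%, with 15 ± 7.0 points. Direction and size are both visible.

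**Clustering in the experience sub-analysis.** From the documents: 15 to 20 users (5.5). Assumed: 100 user surveys, spread evenly over users; users split 60/40 by experience; ratings cut from a normal latent scale to the base split 5/10/20/35/30; latent ICC 0.05 to 0.6; no true difference. Simulated type I error of the ordinary chi-square at nominal 5%:
- 15 users: about 6% at ICC 0.05, rising to about 33% at ICC 0.6.
- 20 users: about 6%, rising to about 24%.

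Repeat simulations move these by a point or two.

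**Cost in precision.** The design effect is 1 + (100/m − 1) × ICC for m users, with half-width 1.96 × √(0.25 / effective n). ICC here is for the favourable/not-favourable response and is assumed to be 0.05 to 0.30.

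| Users | Design effect | Effective n | Half-width, points |
|---|---|---|---|
| independent ratings | 1.0 | 100 | 9.8 |
| 15 | 1.28 to 2.7 | 77.9 to 37.0 | 11.1 to 16.1 |
| 20 | 1.2 to 2.2 | 83.3 to 45.5 | 10.7 to 14.5 |

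**The case against.** The strongest reply is that the endpoint is the median, and 9.4.3 reports it for every question. In the mirror example the medians are 4 and 2, so nobody would mistake dislike for approval. A reader might infer from the identical p-values that the trial could not tell the two apart. The documents do not support that: the p-value is uninformative, but the reported median carries the direction. Nor does any stopping rule rest on these tests; the pause rule in 9.4.5 concerns adverse events only.

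It is also fair to say that equal category frequencies are not the plan's null. The plan names none, and the subgroup sentences make a contingency test an equally available reading. The accurate criticism is that null and contrast are unspecified, and that neither reading tests 9.1. If the chi-square was meant only for subgroups, the hypotheses in 9.1 have no test at all. The general allowance in 9.4.1 for non-parametric corrections does not help, since chi-square is already non-parametric and no reference value is given.

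A further tempting inference is that an ordinary rank test would repair the experience sub-analysis and gain power. It would not as it stands. Under the clustered set-up with 15 users, an unclustered rank test has type I error of about 17%, 26% and 33% at ICC 0.2, 0.4 and 0.6. A valid user-level test of an assumed 0.5 SD latent shift has only roughly 15% to 50% power over ICC 0.05 to 0.6.

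Two caveats on the facts. The documents never expressly equate the Device Use Survey with the Quality Use Survey, though both concern device use. And the survey is daily in 1.3 and 8.1 but per use in 8.2, so the number of user ratings is not fixed.

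**Conclusion.** The point holds in this form. The chi-square in 9.4.3 has no stated null or comparator, and under either natural reading its p-value is uninformative about the one-sample, directional hypotheses in 9.1. This follows from the text; the 32.5 only illustrates it, on assumed counts and an assumed equal-category null. The conflict between 9.4.1 and 9.4.3 is plain on the page.

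The size of the clustering problem depends on assumptions that the documents do not settle: the ICC, the number of user surveys and the split by experience. At ICC 0.05 inflation is negligible; at 0.6 the error rate is about five to seven times nominal.

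These are secondary survey endpoints in a feasibility study and the repair is cheap, so the change should be made, but the trial's primary conclusions do not depend on it.

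**What to change.** In 9.4.3:
- Delete the one-group chi-square.
- For each item report category counts, median and IQR, and the proportion of ratings in the direction stated in 9.1, with a 95% CI. Fix the cut-point in advance, for example the agree categories for comfort. For user surveys the interval should allow for clustering by user.
- For user-survey sub-analyses, use an ordinal or rank method that accounts for the user cluster, and label the experience comparison exploratory.

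In 9.4.1, replace the continuous-scale bullets with the same ordinal summaries.

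The cost is SAP wording and a little more analysis; no extra patients, procedures or data are needed. User-survey intervals will be wider (about 11 to 16 points either side rather than 9.8, with 15 users and ICC 0.05 to 0.30), and the experience sub-analysis will have low power. The favourable proportion adds a dichotomised measure beside the median endpoint, which is why its cut-point must be set beforehand.

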Patient Subject Experience Survey: The patient subject's randomized to device use will be asked in the recovery room post-procedure or receive a phone call or email with REDCap survey link from a qualified study coordinator to answer a short patient experience survey where the data will be collected in REDCap and subsequently transcribed into CTMS. Data collected will include: 1) overall comfort in the device, 2) sensation of increased anxiety, 3) sensation of claustrophobia, 4) perceived safety in the device, 5) any difficulties seeing or hearing while in the device, 6) any additional comments or suggestions regarding the experience in the device. All data will be collected on a Likert scale and stored in CTMS.

Patient subjects' medical records medical will be accessed as part of the study. Personal and medical data collected as part of the study will be stored in a de-identified fashion on an institutionally secured and managed network drive and/or computer.

As part of this study, user subjects' medical records will NOT be accessed. Personal data including age, and gender, will be collected as part of the initial data collection instrument and stored in de-identified fashion on an institutionally secured and managed network drive and/or computer.

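### The patient survey judges anxiety and claustrophobia by a median Likert rating, which cannot show a harm in a minority; the percentage affected should be reported as well (minor, cheap to fix)

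*Combined protocol and SAP*

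**What the plan says.** The synopsis (section 1.1) defines secondary endpoint 3 as "Median Likert rating of the patient questionnaire results to assess patient experience in the device". Section 9.1 states this expectation: "the median Likert ratings of the patient experience post-survey will indicate overall good user comfort and low levels of anxiety or claustrophobia". It gives no numerical criterion.

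Section 8.1 lists the survey content. Anxiety and claustrophobia are separate items: "2) sensation of increased anxiety, 3) sensation of claustrophobia, 4) perceived safety in the device". Only patients "randomized to device use will be asked in the recovery room post-procedure" (or by phone or email) complete it, so there are no surveyed controls.

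For the analysis of each question, section 9.4.3 item 3 states: "Patient experience survey results are collected as ordinal data on a Likert scale. Data will be presented as the median value with standard deviation". The summed score is handled in the same way. It continues: "Statistical significance will be determined using Chi-square test. Sub-analysis will be performed based on patient age, gender, co-morbid conditions, type of airway procedure performed". No comparison is named for the test. Section 9.4.1 adds "the mean comfort/experience level calculated as well as the range" for patient comfort and experience. The same section plans percentages for healthcare burden ("the percentage for each burden subtype will also be identified") but none for patient anxiety or claustrophobia.

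The safety analysis runs separately. Section 8.3.2.3 lists patient claustrophobia and patient anxiety as expected AEs. Section 8.3.3 names the quality use survey and the patient survey as the instruments for recording adverse effects. Section 8.1 has the Quality Use Survey collect the provider's perception of patient anxiety or claustrophobia as safety data. Section 9.4.2 item 2 breaks the AE total down by specific event.

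**The concern.** Section 2.3.1 describes claustrophobia and anxiety as a small risk that this study will assess. A harm expected in a minority is the case that a median handles worst, because the median does not respond until about half of the patients are affected. The natural question is how many device patients felt anxious or claustrophobic, and no planned survey summary answers it. The survey-based statement on a named patient risk could therefore read much the same at quite different rates of harm.

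**Working it through.** **Inputs.** 100 device patients (section 1.3). The survey form is not in the documents, so the following are assumptions: a 5-point item scored 1 (no problem) to 5, with 4 or 5 counted as affected. The rates below are illustrative.

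**The plan's own figure.** The plan gives none for this endpoint. The nearest is section 9.2, whose worked line is 1.96² × 0.25 / 0.1² = 3.8416 × 0.25 / 0.01 = 96.04, rounded up to 97. That reproduces. It is a precision calculation for a proportion with a 10% margin, which suits the summary proposed below.

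**1. Median alone.** With n = 100 the median is the average of the 50th and 51st ordered answers. If at most 49 patients rate 4 or 5, both middle answers can lie in the favourable range.
- 100 answers of 1: median 1, none affected.
- 51 answers of 1 and 49 of 5: median 1, 49 affected.

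So 49 is the mathematical limit, not a forecast.

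**2. How likely is an unaffected median (3 or below)?** It needs X ≤ 49, with X ~ Binomial(100, p).
- p = 0.30: 0.99998.
- p = 0.40: 0.9729.

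A strictly favourable median (2 or below) needs affected plus neutral answers to total at most 49. With 30% affected and 20% neutral, the chance is 0.4602, so neutral answers weaken the effect.

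**3. Median, mean, SD and range together.** Take two sets of counts in categories 1 to 5:

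| Set | Counts | Sum | Sum of squares | Affected |
|---|---|---|---|---|
| A | 7, 45, 38, 1, 9 | 260 | 770 | 1 + 9 = 10 |
| B | 3, 65, 2, 29, 1 | 260 | 770 | 29 + 1 = 30 |

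Both have mean 260/100 = 2.60, SD √((770 − 676)/99) = 0.974, median 2 and range 1 to 5. The exact (Clopper-Pearson) 95% CIs are 4.9% to 17.6% for 10/100 and 21.2% to 40.0% for 30/100, and they do not overlap.

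These sets were constructed to match. In simpler patterns the other summaries do move. With unaffected patients at 1 and affected patients at 4:

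| Affected | Median | Mean | SD |
|---|---|---|---|
| 10 | 1 | 1.30 | 0.90 |
| 25 | 1 | 1.75 | 1.31 |
| 49 | 1 | 2.47 | 1.51 |

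**4. Chi-square.** The plan names no comparison, so two readings are tried.
- Against equal spread (20 per category), set A gives 1600/20 = 80 and set B gives 3080/20 = 154. Set B reversed (1, 29, 2, 65, 3; 68 affected) also gives 154, so the statistic ignores direction.
- Between two subgroups of 50, it is 0 for 5/50 versus 5/50 and also 0 for 15/50 versus 15/50. It tests difference, not level.

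**The case against.** The strongest reply is that the safety analysis already covers this. Both harms are expected AEs, the AE definition in section 8.3.1.1 is broad, the patient survey is a named recording source, the provider survey is a second source, and section 9.4.2 counts by type as part of a primary endpoint. Dividing by the number of device patients then gives a percentage. This largely stands: the harm is not left to the median alone. What remains is that no text says which Likert answer becomes an AE, and a provider's perception is not the patient's report. The AE count may therefore differ from the patient-reported proportion.

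A second reply is that the SD, mean and range would reveal a problem. Often they would. A reader might infer from the 0-to-49 result that the plan as a whole cannot tell no harm from harm in nearly half the patients. The documents do not support that. The result concerns the median alone, and the section 9.4.1 range, if applied to these items, separates those two cases, because its maximum reaches 4 or 5 once anyone is affected. What survives is narrower: these summaries do not determine the proportion.

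Third, the proportion can be recovered from the counts behind a chi-square test or from the individual listings (section 9.4.7). That is true, but it is not a planned output, and the cut-off for an affected patient would then be chosen after the answers are known.

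**Conclusion.** The point holds as a minor improvement to a secondary endpoint. The plan bases its statement on anxiety and claustrophobia on a summary that cannot show a minority harm, and the accompanying survey summaries do not supply the proportion. The size shown, 10 versus 30 affected of 100 with identical summaries, is a possibility under an assumed 5-point scale and a 4-or-5 cut-off. It is not the expected result.

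A reader might also infer that the trial's safety conclusion or its pause rule is compromised. It is not: no primary endpoint, success rule or stopping rule uses the survey median, and the pause rule in section 9.4.5 looks at AE and ADE totals.

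**What to change.** In section 9.4.3 item 3:
- Pre-specify the adverse response categories for the anxiety and claustrophobia items (for example agree or strongly agree, or the form's equivalent).
- Report the number and percentage of responding device patients in those categories, for each item and for either item, with an exact 95% CI and the full category distribution, beside the AE count by type.
- Base the section 9.1 statement on that proportion, described as uncontrolled, and keep the median as a supplementary line.

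Two additions are optional. A benchmark for a low rate could be fixed in advance as an upper 95% limit. With 100 responders, a limit below 10% allows at most 4 affected (upper limit 9.93%) and below 20% at most 11 (18.83%). With 80 responders the counts are 2 and 8. These benchmarks have no source in the protocol and are for the team to choose. Section 8.3.3 could also say how survey answers are reviewed as possible AEs. That sentence needs care, because more recorded AEs could feed the section 9.4.5 pause rule.

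The cost is SAP wording and one table from data already collected. The downsides are that the result may look less favourable than a median, and that without surveyed controls ordinary pre-operative anxiety cannot be separated from a device effect.
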